19.2.2 Analysis

Population: Table: PK

Listing: PK

Stratification: Table: By part and group

Listing: By part, group, participant, timepoint & parameter

Statistics: PK concentration data will be descriptively summarized using: number of non-missing observations (n), arithmetic mean (Mean), standard deviation (SD), coefficient of variation (CV%), minimum (Min), median (Median) and maximum (Max).

Graphical Presentation: Individual concentration versus time plots; linear and semi-log; using the actual time points by participants, and groups. Overlaying individual concentration time profiles will be displayed.

Mean concentration time plots; linear with standard deviation and semi-log; using scheduled (nominal) time points, and meal group. Error bars should be included only in the linear plots.

PK Parameter Data will be descriptively summarized using number of non-missing observations (N), arithmetic mean (Mean), standard deviation (SD), coefficient of variation (CV%), minimum (Min), median (Median) and maximum (Max), Geometric mean (Geo mean), Geometric coefficient of variation (GCV%).

T_{max} will be summarized by treatment using Min, Max and Median.

Plots for Individual PQP AUC_{0-t} and C_{max} by dose group will be provided.

19.3 Physical examination

19.3.1 Variables and derivations

Following physical examination parameters will be reported & applicable to both part 1 & part 2 of the study:

- Skin
- Lymph Nodes
- Head
- Eyes
- Ear
- Nose
- Throat
- Respiratory
- Cardiovascular
- Abdomen
- Extremities
- Musculoskeletal
- Neurological

19.3.2 Analysis

For the analyses of laboratory parameters, vital signs & ECG parameters refer to sections 16.2 & 17.2 respectively.

Population: Table: NA

Listing: ENRL

Stratification: Table: NA

Listing: By part, group, participant, timepoint & parameter

Statistics: The physical examination assessment will be presented in data listings at all assessment time points. Physical examination data will be classified as normal, abnormal not clinically significant & abnormal clinically significant.

20. Exploratory endpoints

20.1 PK profile and PK parameters for Piperaquine N-oxide metabolite

20.1.1 Variables and derivations

The following pharmacokinetic parameters will be calculated for N-oxide PQP (metabolite), whenever possible:

- C_{max} : Maximal plasma concentration
- T_{max} : Time at which the maximum plasma concentration occurs
- $t_{1/2}$: Terminal elimination half-life
- $AUC_{0-\infty}$: Area under the plasma concentration-time curve from time 0 extrapolated to infinite time
- AUC_{0-t} : Area under the plasma concentration curve from time zero up to the last quantifiable concentration
- AUC_{0-24h} : Area under the plasma concentration curve from time zero to 24 hours
- AUC_{0-72h} : Area under the plasma concentration curve from time zero to 72 hours
- AUC_{0-168h} : Area under the plasma concentration curve from time zero to 168 hours
- $\%AUC_{extrap}$: Percentage of AUC that is due to extrapolation from t_{last} to infinity
- λ_z : Terminal rate constant

20.1.2 Analysis

Population: Table: PK

Listing: PK

Stratification: Table: By part and group

Listing: By part, group, participant, timepoint & parameter

Statistics: PK concentration data will be descriptively summarized using: number of non-missing observations (n), arithmetic mean (Mean), standard deviation (SD), coefficient of variation (CV%), minimum (Min), median (Median) and maximum (Max).

Graphical Presentation: Individual concentration versus time plots; linear and semi-log; using the actual time points by participants, and groups. Overlaying individual concentration time profiles will be displayed.

Mean concentration time plots; linear with standard deviation and semi-log; using scheduled (nominal) time points, and meal group. Error bars should be included only in the linear plots.

PK Parameter Data will be descriptively summarized using number of non-missing observations (N), arithmetic mean (Mean), standard deviation (SD), coefficient of variation (CV%), minimum (Min), median (Median) and maximum (Max), Geometric mean (Geo mean), Geometric coefficient of variation (GCV%).

T_{max} will be summarized by treatment using Min, Max and Median.

Plots for Individual PQP N-oxide (metabolite) AUC_{0-t} and C_{max} by dose group will be provided.

20.2 To evaluate the palatability of the new PQP granule formulation in healthy adult participants.**20.2.1 Variables and derivations****Variables:**

All the 3 questions (including sub-domains) and numerical answers (from 1 to 5) to these will be considered from the eCRF page of the Palatability Questionnaire [PALAQ].

20.2.2 Analysis

Population: Table: SAF

Listing: ENRL

Stratification: Table: By part and group

Listing: By part, group and participant

Statistics: The questionnaire data will be presented in data listings and summarised as frequency and percentages (n and %).

21. Revision history

Version	Date	Change
1.0	19-DEC-2023	Initial document

22. Appendix 1: Programming Conventions for Tables, Data Listings, and Figures (TLFs)
22.1 Paper Size, Orientation, and Margins

The margin, page size, and line size specifications as stipulated in Table 22.1 will be used for the presentation of all TLFs.

Table 22.1: Output margin, page size, and line size specifications

	Landscape	Portrait
Margins (Inches):		
Top	1.25	1
Bottom	1	1
Left	1	1.25
Right	1	1
Header (Inches)	0.5	0.5
Footer (Inches)	0.5	0.5
SAS® specifications:		
PAGES	46	67
LINE SIZE	134	93

22.2 Fonts

The font type “Courier New” should be used as a default for tables and data listings, with a font size of 8. The font color should be black. No bolding, underlining, or italics are permitted.

Figures should have a default font of “Times Roman”, “Helvetica” or “Courier New”.

22.3 Header Information

Headers should be defined as follows:

- The header should be placed at the top of the page (same place on each page).
- The sponsor's name should appear in row 1, left-aligned.
- The word “CONFIDENTIAL” should appear in row 1, right aligned.
- The protocol number should appear in row 2, left-aligned.
- The page identification in the format Page X of Y (where Y is the total number of pages for the TLF) should appear in row 2, right aligned.
- The TLF identification number should appear in row 3, centered.
- The TLF title should start in row 4, centered.

- The TLF population should appear in row 5, centered. The population should be spelled out in full, e.g., the *Safety analysis population* in preference to the *Safety analysis population*.
- Row 6 should be a continuous row of underscores ('_') (the number of underscores should equal the line size).
- Row 7 should be a blank line.
- Mixed cases should be used for titles.
- Titles should not contain quotation marks or footnote references.
- The column headings should be underlined with a row of underscores ('_').
- Column headings spanning more than one column should be underlined and have underscores on either side of the title and should be centered.
- Column headings containing numbers should be centered.
- Column headings should be in mixed case.
- In general, the analysis population count should appear in the column header in the form "(N=XX)".

22.4 Table and Data Listing Table, Listing and Figure (TLF) Conventions

22.4.1 General

- The first row in the body of the table or data listing should be blank.
- The left-hand column should start in Column 1. No indenting or centering of the TLF should occur.
- Rounding should be done with the SAS® function ROUND.
- Numerical values in tables should be rounded, not truncated.
- Numerical values should be decimal point aligned.
- Text values should be left aligned.
- The first letter of a text entry should be capitalized.
- The study drug should appear first in tables with the treatment group as columns.
- All variables contained on the eCRF (which have data present) should appear in the data listings, along with all derived data appearing in the corresponding tables.
- The width of the TLF should match the line size.

22.4.2 Univariate statistics

- Statistics should be presented in the same order across tables (i.e., n, mean, SD, minimum, median, and maximum).

- If the original data has N decimal places, then the summary statistics should have the following decimal places:
 - Minimum, maximum, and CV (%): N
 - Mean and median: N + 1.
 - SD: N + 2.

22.4.3**Frequencies and percentages [n, (m) and %]**

- Mentions should be reported inside parentheses, with one space between the count and the left parenthesis of the mentions. An example is given below:
 - 124 (645)
- Percent values should be reported inside parentheses, with one space between the right parenthesis of the mention and the left parenthesis of the percentage. Parentheses should be justified to accept a maximum of 100.0 as a value and padded with blank space if the percent is less than 100.0. An example is given below:
 - 77 (156) (100.0)
 - 50 (56) (64.9)
 - 0 (0) (0.0)
- Percentages will be reported to one decimal place, except percentages <100.0 but >99.9 will be presented as '99.9' (e.g., 99.99 is presented as >99.9); and percentages <0.1 will be presented as '<0.1' (e.g., 0.08 is presented as <0.1). Rounding will be applied after the <0.1 and >99.9 rules.
 - (<0.1)
 - (6.8)
 - (>99.9)
- Percentages may be reported to 0 decimal places as appropriate (for example, where the denominator is relatively small).
- Where counts are zero, mentions of 0 and percentages of 0.0 should appear in the table.

22.4.4**Confidence intervals (CIs)**

- CIs should be presented with one additional decimal place as that of the raw data, and SDs and standard errors (SEs) with two additional decimal places as that of the raw data.
- CIs should be justified so that parentheses are displayed on consecutive lines of a table "line up".

22.4.5 P-values

- P-values should be reported to four decimal places.

22.4.6 Ratios

- Ratios should be reported with one additional decimal place as that of the raw data.

22.4.7 Spacing

- There should be a minimum of 1 blank space between columns (preferably 2).

22.4.8 Missing values

- A “0” should be used to indicate a zero frequency.
- A blank will be used to indicate missing data in data listings.

22.5 Figure output conventions

Figures should be provided in RTF files using the SAS® Output Delivery System (ODS).

22.6 Dates and times

Depending on the data available, dates and times will take the form ddMMMyyyy and hh: mm.

22.7 Spelling format

The spelling format to be used is English US.

22.8 Presentation of treatment groups

- Part 1
 - Group 1 (PQP Hard Tablet - Fasted)
 - Group 2 (PQP Dispersible Granules - Fasted)
- Part 2
 - Group 3 (PQP Dispersible Granules - High-fat Meal)
 - Group 4 (PQP Dispersible Granules - Low-fat Meal)
 - Group 5 (PQP Dispersible Granules - Whole Milk 250ml)

22.9 Presentation of visits

- Screening

- Day -1 (Admission)
- Day 1
- Day 2
- Day 3
- Day 5
- Day 8
- Day 15
- Day 22
- Day 30

23. Appendix

23.1 Appendix 1: Partial date conventions for adverse events and prior and concomitant medication

Event	Missing	Imputation
Start Date	Day	If event start Month = Treatment start month and event start Year = Treatment start Year, then event start Day= minimum of (Treatment Start Day or event end Day). Otherwise, event start day = "01".
	Day and Month	If event start Year = Treatment start Year, then event start Day and Month = minimum of (Treatment Start Day and Month or event end Day and Month). Otherwise, event start Day and Month = "01 Jan".
	Day, Month and Year	No Imputation will be performed.
End Date	Day	If event End Month = Study conclusion Month and event End Year= Study conclusion Year, Then event End Day= Study Conclusion Day. Otherwise, event End Day = last day of respective month.
	Day and Month	If event End Year = Study Conclusion Year, then event End Day and Month = Study Conclusion Day and Month. Otherwise, event End Day and Month = "31 Dec".
	Day, Month and Year	No Imputation will be performed.

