Comparator	Reference therapy: PQP hard tablet 320 mg; single dose (320 mg) given orally with 240 ml of water.
Number of Participants	This is a pilot BA/FE study, and the sample-size is not based on formal statistical considerations. The number assigned to each treatment Group (n=12) is considered adequate to characterise the PK of the prototype formulation of PQP in various study conditions.
Study Duration	4 to 6 Months.
Study Schedule	First Participant In (JULY-2023); estimated Last- Participant Out (DECEMBER-2023)
Study Centre	Single-centre: Bagamoyo Clinical Trials Unit, IHI – BRTC.

Statistical Considerations	
This pilot Phase 1 trial is not designed to test specific hypotheses. The trial is intended to determine the PK parameters of the prototype formulation dispersion granules of PQP in fasting state (Part 1) and to provide a preliminary assessment of the effect of various fed states (Part 2) on the systemic exposure of PQP.
 
The Safety analysis set will consist of all randomised participants who received the study product. The PK analysis set will consist of those participants in the safety set who have sufficient blood samples taken for at least one of the PK variables to be calculated.
 
The statistical methods and reporting will follow ICH E9 and international recommendations, including CONSORT. A statistical analysis plan (SAP) containing detailed statistical methodology will be written and signed off before the database hard lock. The plan may be updated to reflect adaptive features of the trial as appropriate.

GCP Statement	
This study will be conducted in compliance with the protocol, the current version of the Declaration of Helsinki, ICH-GCP E6(R2) as well as all Tanzanian legal and regulatory requirements as stipulated by NaTHREC and TMDA.

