### 2.1.5 Safety profile and potential risks

Although transient asymptomatic alanine aminotransferase/aspartate aminotransferase (ALT/AST) elevations have been described, including in Phase 1 participants, these are generally mild in severity and considered as uncommon. PQP is known to induce QTc prolongation in human participants (11, 12). The following aspects of the PK and adverse event (AE) profiles of PQP, were considered in determining the Inclusion and Exclusion criteria and in designing the tolerability and safety monitoring of this study:

- PQP is known to cause a QTc interval prolongation, and this effect is concentration-related,
- PQP has a terminal elimination half-life of approximately 22 days, however, approximately 1% of the plasmatic Cmax is predicted at 672 hours (i.e. 28 days) after the administration of 1280 mg in healthy adults (13). Therefore, a follow-up of 30 days is considered acceptable to ensure that possible delayed effects on safety laboratory tests are appropriately documented.

As precautionary measures pertaining to QTc effects of PQP, the European Medicines Agency (EMA) has advised that:

- DHA-PQP (Eurartesim®), not be administered with a meal to avoid food-induced increase in PQP Cmax and consequently possible clinically relevant QTc prolongation,
- Baseline and post-dose electrocardiograms (ECGs) be obtained,
- Recent exposure to concomitant drugs known to induce QTc prolongation be avoided (10,14).

Therefore, during this study, healthy participants with risk factors for QTc prolongation will be excluded and enrolled participants will be monitored for QTc effects through ECG recording.

Clinical monitoring will include periodic biochemistry and haematology measurements as well as regular physical examination and AE recording.

Participants will remain in the Unit under medical supervision until 48 hours following the investigational medicinal product (IMP) administration and will be followed up to Day 30 (+/-1 day).

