## 8.8 Follow-up observation for study participants with adverse reactions

All AEs must be documented and followed up until the event is either resolved or a satisfactory explanation is found, or the investigator considers it medically justifiable to terminate the follow-up.

Spontaneously reported SAEs will be collected until 30 days following the final study visit. SAEs experienced after this 30-day period will only be reported if the investigator suspects a causal relationship with the study drug.

If a study participant experiences a clinically significant finding or a worsening of an ongoing medical condition after signing the Informed Consent, the event will be recorded as an adverse event.

Any AEs that are unresolved at the participant's last AE assessment in the study (i.e. at the follow up visit) are to be followed up by the Investigator for as long as medically indicated. MMV retains the right to request additional information for any participant with ongoing AE(s)/SAE(s) at the end of the study, if judged necessary.

The Investigator will decide on

- Study drug discontinued
- Healthy participant withdrawn from study
- Concomitant Medication required
- Hospitalization required or prolonged (this should also be reported as an SAE)
- Other

The PI or delegate will follow up all AEs wherever possible until the symptom has resolved or stabilised. The date of confirming outcome will be recorded. The course of AEs will be assessed by reference to the following as a guide.

- Recovered: The AE has resolved and the participant returned to his condition prior to onset.
- Recovered with sequelae: The AE resolved, but the participant has sequelae.
- Recovering: The AE has almost resolved and the participant is returning to his condition prior to onset.
- Death: The study participant died. Causal relationship is no object.
- Ongoing: Even on the final day of observation the AE had not resolved and the participant's condition remained unchanged. In case of death, the participant died of other causes not related to the AE from which there was no recovery.

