14.1 Variables and derivations

Concomitant medications will be coded using the WHO-DD, dated 1 March 2023, or higher.

Prior medications are defined as any medication taken before the first administration of the study treatment.

'Concomitant medications' are defined as any medication taken after the first administration of the study treatment.

In section 23 of Appendix 1, the algorithm is given for the calculation of partial date imputation for prior and concomitant medications, and it will be used for partially missing prior and concomitant medications, start and end date imputation.

The following parameters will be summarised for concomitant medications:

- Number of participants with at least one prior and concomitant medication
- Number of participants for each prior and concomitant medication by ATC and PT.

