15.1 Variables and derivations

Adverse Events (AEs) will be coded using MedDRA central coding dictionary, version 26.0 or higher.

For the definition of Adverse events (AE) and Serious adverse events (SAE) refer to the protocol sections 8.1.2 & 8.4.

Pre-treatment adverse-events are defined as AEs between informed consent and IMP administration.

Treatment-emergent adverse events (TEAEs) are defined as an event that emerges during treatment, have been absent pre-treatment or worsens relative to the pre-treatment state.

The following parameters will be summarised for the participant's adverse events as mentioned in eCRF:

- All Adverse Events
- Number of participants with at least one Pre-Treatment AE
- Number of participants with at least one TEAE
- Number of participants with at least one study drug-related TEAE
- Number of participants with at least one serious TEAE
- Number of participants with at least one study drug-related serious TEAE
- Ongoing AEs
- TEAEs by Toxicity Grade
- TEAEs by Outcome
- TEAEs by Action Taken with Study Treatment
- TEAEs by Relationship
- TEAEs leading to Death.
- TEAEs leading to withdrawn or discontinued the study.

Derivations:

- The question on eCRF page Adverse Events "Relationship to investigational product" is answered "Related/Suspected", then respective AEs will be considered as drug-related AEs.
- If The question on eCRF page Adverse Events "Was the adverse event serious" is answered as "YES" then the respective AE will be considered as serious AE.
- The question on eCRF page Adverse Events "Was the adverse event serious" is answered as "YES" and answered as "Related/Suspected" then respective AEs will be considered drug-related SAEs.

- If the seriousness criteria are “RESULTS IN DEATH” then we will consider it as AE leading to death.
- participant’s primary reason for discontinuation is “ADVERSE EVENT” then we will consider it as AE leading to withdrawal/discontinued from the study.

Imputations will only be performed where at least the year is provided. The imputations derived for partial dates will be as per appendix 1.

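### The SAP's partial-date rule compares bare day numbers, so an AE that ends in the month after dosing can be given an onset date before dosing

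*SAP*

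**What the plan says.** The start-date rules are in the partial-date table of SAP 23.1.

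- **Day missing.** If the onset month and year equal those of treatment start, "then event start Day= minimum of (Treatment Start Day or event end Day"). Otherwise the day is set to 01. Nothing requires the event to end in the dosing month.
- **Day and month missing.** If the onset year equals the treatment year, "event start Day and Month = minimum of (Treatment Start Day and Month or event end Day and Month"). Otherwise 01 January is used. This row compares day with month but leaves out the year.

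SAP 15.1 sends AE dates to this table: "The imputations derived for partial dates will be as per appendix 1". The same section defines the pre-treatment category by time: "Pre-treatment adverse-events are defined as AEs between informed consent and IMP administration". It defines TEAEs in words, as events that emerge or worsen under treatment, and does not say which date sets the flag. No other part of the SAP says that an AE with unclear onset counts as treatment-emergent.

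SAP 14.1 uses the same table for medications; concomitant medications "are defined as any medication taken after the first administration of the study treatment".

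**The concern.** A minimum of two day numbers gives the earlier date only when both days lie in the same month. In this trial they often need not. Recruitment is rolling (Protocol 5.2), each participant gets a single dose, and Protocol 2.1.5 says participants "will be followed up to Day 30 (+/-1 day"). Many follow-up periods therefore cross a month end.

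In the affected case nothing shows that the AE began before dosing, yet the rule places it there. If the imputed date drives the flag, the AE leaves the TEAE and drug-related TEAE tables even where the investigator judged it related. It moves to the pre-treatment table or, if the imputed date precedes consent, fits neither category. The error runs in one direction only, and AE occurrence is a secondary endpoint. With 12 participants per group, one participant moved is 1/12 = 8.3 percentage points of that group's incidence.

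**Working it through.** The plan gives no figure to reproduce here, so the check applies the rule as written.

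**Inputs.** The rule is from SAP 23.1. Follow-up runs to Day 30 (SAP 7.3), with a one-day visit window (Protocol 2.1.5). The calendar comes from the Protocol synopsis: "First Participant In (JULY-2023); estimated Last- Participant Out (DECEMBER-2023"). Assumptions: dosing on any day from 1 July to 31 December 2023, onset day missing, onset month equal to dosing month, end date known.

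**Worked case.** Dose 20 November, onset November, end 5 December. The rule gives min(20, 5) = 5, so onset is 5 November, 15 days before dosing. Comparing complete dates gives 20 November.

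**Why it is systematic.** Let L be the length of the dosing month and k the days from dosing to the end date. For an end in the next month, end day number = dosing day + k − L. The rule therefore moves onset L − k days before dosing whenever k < L. Day 30 is k = 29, and every month from July to December has at least 30 days, so every next-month end by Day 30 is affected. In the worked case L − k = 30 − 15 = 15.

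**Enumeration of dosing/end date pairs.**

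| End dates considered | Later-month ends imputed before dosing |
|---|---|
| To Day 30 | 2,610 of 2,610 (by 1 to 30 days, median 10) |
| To Day 30, last dose 2 December | 2,175 of 2,175 |
| To Day 31 | 2,730 of 2,790 (97.8%) |
| To Day 60, next-month ends only | 2,730 of 5,632 (48.5%) |
| To Day 60, any later month | 5,224 of 8,126 (64.3%) |

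The 2 December limit puts Day 30 on 31 December, inside the planned schedule. The Day 60 rows are relevant because unresolved AEs "are to be followed up by the Investigator for as long as medically indicated" (Protocol 8.8).

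**Not affected.** Of all 5,520 pairs from Day 1 to Day 30, the other 5,520 − 2,610 = 2,910 end in the dosing month, and none is misplaced. AEs with onset in a later month (set to day 01) and AEs whose end day number equals or exceeds the dosing day are also safe.

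**Day-and-month row.** Dose 20 December 2023, end 10 January 2024: the minimum of 20 December and 10 January is 10 January, placed in 2023. That is 344 days before dosing, outside the 45-day screening window. All 435 pairs with December 2023 dosing and a January 2024 end by Day 30 land more than 45 days before dosing. This case needs the study to run past its planned December 2023 end.

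**With complete dates compared.** Over end dates from 20 days before dosing to Day 60 (14,720 pairs), no pair with an end on or after dosing is placed before dosing. An AE that ended before dosing, such as on 5 November, keeps its pre-dose date.

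**The case against.** The arithmetic is not in dispute; consequence and frequency are.

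- **The flag.** SAP 15.1 defines TEAEs by substance and never says that the imputed date decides. This stands as a limit: loss from the TEAE tables is an inference. It is a sound one, because the SAP sends AE partial dates to this table, defines pre-treatment AEs by time, and plans no AE duration or time-to-onset summary that would otherwise need an imputed onset.
- **Rarity.** Several conditions must coincide. Participants stay in-house to Day 3 and are then seen on Days 5, 8, 15, 22 and 30; onset date is a required AE item (Protocol 8.7) and entries are checked by monitors (Protocol 9.2). This stands: the expected number of affected AEs is small, and the documents give no count.
- **The counts.** Full agreement to Day 30 follows from month lengths and says nothing about frequency. Short AEs cross a month end less often: with dosing from 1 July to 2 December, ends by Day 3 give 15 affected pairs of 465 (3.2%) and ends by Day 8 give 140 of 1,240 (11.3%). This also stands.
- **Ongoing AEs.** The table does not say what the minimum is when there is no end date. Treating those AEs as unaffected assumes a default to the dosing day, which the fix should state.
- **Low stakes.** Safety analysis is descriptive (SAP 7.5), and the AE stays in the all-AE listing (SAP 23.2). That limits the harm but does not make the imputed date right.
- **A sensible programmer.** Someone might compare complete dates anyway. The text does not ask for it, and the next row, which names day and month, suggests that the first row means day numbers alone.

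**Conclusion.** The concern holds. As written, the day-missing rule gives a pre-dose onset to every AE with onset known only as the dosing month and a known end in the next month by Day 30 (2,610 of 2,610 date pairs under July to December 2023 dosing). The day-and-month row fails in the same way across a year end.

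The error in the imputed date rests on the SAP's wording alone. The effect on TEAE tables rests on the further assumption that the imputed date sets the flag. Few AEs are likely to be involved. Medications that end after dosing remain concomitant under SAP 14.1 and at most are also counted as prior. The primary PK analysis is not affected. The rule should be corrected because it is wrong as stated, can bias safety counts in only one direction, and costs almost nothing to repair.

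**What to change.** In both start-date rows of SAP 23.1, when the known parts match treatment start, impute onset as the earlier of the complete treatment start date and the complete event end date (day, month and year). Use the treatment start date if there is no end date. Keep the existing first-of-month and 01 January rules for all other cases.

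Add one sentence to SAP 15.1: an AE not shown to have started before dosing is treatment-emergent. The date correction works without this sentence, but the sentence settles how the flag is set.

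The cost is two table cells, one sentence and one line of code, with no new data. Protocol 10.4 allows the SAP to be updated and requires sign-off before the database hard lock. A change made as a departure from the signed plan would have to be reported and justified under Protocol 10.11.
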